9.7. Reporting to the Research Ethics Committee

9.7.1. Unexpected and Related Serious Adverse Events

BCTU will report all events categorised as Unexpected and Related SAEs to the main Research Ethics Committee (REC) and RGT within 15 days.

9.7.2. Other safety issues identified during the course of the trial

The main REC and RGT will be notified immediately if a significant safety issue is identified during the course of the trial.

9.8. Investigators

Details of all Unexpected and Related SAEs and any other safety issue which arises during the course of the trial will be reported to PI. A copy of any such correspondence should be filed in the site file and TMF.

9.9. Trial Oversight Committee

The independent TOC will review all individual SAEs and associated actions.

10. DATA HANDLING AND RECORD KEEPING

10.1. Source Data

In order to allow for the accurate reconstruction of the trial and clinical management of the subject, source data will be accessible and maintained. Source data is kept as part of the participants' medical notes generated and maintained at site.

10.2. Case Report Form (CRF) Completion

CRFs will be completed by research staff via the eRDC system. Data reported on each form will be consistent with the source data and any discrepancies will be explained. All missing and ambiguous data will be queried. Staff delegated to complete CRFs will be trained to adhere to CRF completion guidelines. This training will include:

- CRF completion and corrections
- Date format and partial dates
- Time format and unknown times

IRAS ID: 253447

- Rounding conventions
- Trial-specific interpretation of data fields
- Entry requirements for concomitant medications (generic or brand names)
- Which forms to complete and when
- What to do in certain scenarios, for example when a subject withdraws from the trial
- Missing/incomplete data
- Completing SAE forms and reporting SAEs
- Repeat laboratory tests
- Protocol and GCP non-compliances

In all cases it remains the responsibility of the site's Principal Investigator to ensure that the CRF has been completed correctly and that the data are accurate. Where applicable for the trial this will be evidenced by the signature of the site's Principal Investigator or delegate(s) on the CRF.

10.3. Data Management

Processes will be employed to facilitate the accuracy of the data included in the final report. These processes will be detailed in the trial specific data management plan. Coding and validation will be agreed between the trial manager, statistician and programmer and the trial database will be signed off once the implementation of these has been assured. Trial data will be inputted directly into the database by the site from source data. All missing and ambiguous data will be queried by BCTU using data clarification forms (DCFs), which will be conducted on a monthly basis. Sites will be expected to resolve these queries within 4 weeks, and will be responsible for amending any incorrect data in the database. Any self-evident corrections will be identified and documented on a self-evident corrections form. Permission will be sought from the site's Principal Investigator before any of these self-evident changes are made to the trial data by a BCTU staff member.

10.4. Data Security

The security of the System is governed by the policies of the University of Birmingham. The University's Data Protection Policy and the Conditions of Use of Computing and Network Facilities set out the security arrangements under which sensitive data should be processed and stored. All studies at the University of Birmingham have to be registered with the Data Protection Officer and data held in accordance with the General Data Protection Regulation (GDPR) 2018. The University will designate a Data Protection Officer upon registration of the study. The Study Centre has arrangements in place for the secure storage and processing of the study data which comply with the University of Birmingham policies.

The System incorporates the following security countermeasures:

- Physical security measures: restricted access to the building, supervised onsite repairs and storages of back-up tapes/disks are stored in a fire-proof safe.
- Logical measures for access control and privilege management: including restricted accessibility, access controlled servers, separate storage of non-identifiable data etc.
- Network security measures: including site firewalls, antivirus software, separate secure network protected hosting etc.
- System Management: the System shall be developed by the BCTU Programming Team and will be implemented and maintained by the BCTU Programming Team.

- System Design: the system shall comprise of a database and a data entry application with firewalls, restricted access, encryption and role based security controls.
- Operational Processes: the data will be processed and stored within the Study Centre (University of Birmingham).
- Data processing: Statisticians will only have access to anonymised data.
- System Audit: The System shall benefit from the following internal/external audit arrangements:
 - Internal audit of the system
 - Periodic IT risk assessment
- Data Protection Registration: The University of Birmingham has Data Protection Registration to cover the purposes of analysis and for the classes of data requested. The University's Data Protection Registration number is Z6195856.

10.5. Archiving

It is the responsibility of the PI to ensure all essential trial documentation and source documents (e.g. signed ICFs, Investigator Site Files, Pharmacy Files, participants' hospital notes, copies of CRFs etc.) at their site are securely retained for at least 25 years. The centrally stored trial Master File will be archived in line with BCTU SOPs.

11. QUALITY CONTROL AND QUALITY ASSURANCE

11.1. Site Set-up and Initiation

The CI is required to sign a UoB CI agreement to document the expectations of both parties. The UoB CI agreement document must be completed prior to participation. The CI is required to sign a Clinical Trials Task Delegation Log which documents the agreements between the CI and BCTU. In addition all local PIs will be asked to sign the necessary agreements including a Site Signature and Delegation log between the PI and the CTU and supply a current CV and GCP certificate to BCTU. All members of the site research team are required to sign the Site Signature and Delegation Log, which details which tasks have been delegated to them by the PI.

Prior to commencing recruitment, each recruiting site will undergo a process of initiation, either a meeting or a teleconference, at which key members of the site research team are required to attend, covering aspects of the trial design, protocol procedures, adverse event reporting, collection and reporting of data and record keeping. Sites will be provided with an Investigator Site File containing essential documentation, instructions, and other documentation required for the conduct of the trial. The BCTU trials team must be informed immediately of any change in the site research team.

11.2. Monitoring

Monitoring will be carried out as required following a risk assessment and as documented in the monitoring plan. Investigators and their host institutions will be required to permit trialrelated monitoring and audits by the SEE U Trial Manager or a member of the trial monitoring team providing direct access to source data and documents as requested. Additional on-site monitoring visits may be triggered, for example by poor CRF return, poor data quality, low SAE reporting rates, excessive number of participant withdrawals or deviations. If a monitoring visit is required the Trials team will contact the site to arrange a date for the proposed visit and will provide the site with written confirmation. Investigators will allow the SEE U trial staff access to source documents as requested. NHS Trusts may also be subject to inspection by internal Research and Development Managers, and should do everything requested by the CI in order to prepare and contribute to any inspection or audit. Study participants will be made aware by the PIS of the possibility of external audits of the data they provide.

11.3. **Onsite Monitoring**

Monitoring is carried out as required following trial specific risk assessment and as documented in the monitoring plan. Any monitoring activities will be reported to the trials team and any issues noted will be followed up to resolution. Additional on-site monitoring visits may be triggered, for example by poor CRF return, poor data quality, low SAE reporting rates, excessive number of participant withdrawals or deviations. If a monitoring visit is required the Trials team will contact the site to arrange a date for the proposed visit and will provide the site with written confirmation. Investigators will allow the SEE-U trial staff access to source documents as requested. The monitoring will be conducted by the SEE-U trial management team.

11.4. Central Monitoring

Trials staff will be in regular contact with the site research team to check on progress and address any queries that they may have. Trials staff will check incoming ICFs and CRFs for compliance with the protocol, data consistency, missing data and timing. Sites will be sent DCFs requesting missing data or clarification of inconsistencies or discrepancies.

Sites will be requested to send in copies of signed ICFs and other documentation for inhouse review for all participants providing explicit consent. This will be detailed in the monitoring plan.

11.5. Audit and Inspection

PROTOCOL

The Investigator will permit trial-related monitoring, audits, ethical review, and regulatory inspection(s) at their site, providing direct access to source data/documents. The investigator will comply with these visits and any required follow up. Sites are also requested to notify BCTU of any relevant inspections.

11.6. Notification of Serious Breaches

The sponsor is responsible for notifying the REC of any serious breach of the conditions and principles of GCP in connection with that trial or the protocol relating to that trial. Sites are therefore requested to notify the Trials Office of any suspected trial-related serious breach of GCP and/or the trial protocol. Where the Trials Office is investigating whether or not a serious breach has occurred sites are also requested to cooperate with the Trials Office in providing sufficient information to report the breach to the REC where required and in undertaking any corrective and/or preventive action.

Sites may be suspended from further recruitment in the event of serious and persistent noncompliance with the protocol and/or GCP, and/or poor recruitment. Any major problems identified during monitoring may be reported to the Trial Management Group, Trial Steering Committee, and the REC. This includes reporting serious breaches of GCP and/or the trial protocol to the REC. A copy is sent to the University of Birmingham Clinical Research Compliance Team at the time of reporting to the REC.

12. END OF TRIAL DEFINITION

The end of trial will be four weeks after the last verified data capture. The BCTU trial team will notify the main REC and RGT that the trial has ended and a summary of the clinical trial report will be provided within 12 months of the end of trial.

A copy of the end of trial notification as well as the summary report is also sent to the University of Birmingham RGT at the time of sending these are sent to the REC.

13. STATISTICAL CONSIDERATIONS

13.1. Sample Size

The estimated sample size for the substantive study will be partially informed by the output from this pilot study but will be sufficiently powered to detect a minimally important reduction in rates of the composite measure. This study will aim to enroll 90 women. This number will allow us to measure the recruitment rate with 95% confidence interval (CI) width of approximately 10% if we assume 270 will be eligible over six months recruitment and we recruit a third of these.

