6. RECRUITMENT, ENROLMENT AND RANDOMISATION

6.1. Recruitment

Patients will be identified by doctors, research nurses and research midwives. All women undergoing a surgical evacuation of products of conception will be considered for the trial. Their clinical notes will be screened in order to ascertain eligibility. Only a member of the patient's existing clinical care team will have access to patient records in order to identify potential participants and check whether they meet the inclusion criteria or make the initial approach to patients.

All participants will be approached and recruited at a recruiting NHS hospital. A patient facing poster advertising the study will be displayed in clinically appropriate areas within the hospital.

Following a recent survey, 320 surgical evacuations are performed on average per year (60 evacuations under local anaesthetic and 260 under general anaesthetic). We will aim to recruit 90 participants in approximately 6 months.

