8.2. Process outcomes

To obtain estimates for important aspects of the protocol to allow development of a substantive trial, specifically:

- 1. To derive real-time data on the design aspects of the study:
 - I. Proportion of eligible women of those screened: this will be the proportion of patients with miscarriage who are approached.
 - II. Proportion of eligible women randomised: this will be the proportion of eligible patients randomised. A conversion rate of less than 33% will be considered unrepresentative and not sufficient to sustain a large study.
 - III. Attrition rates: what is the follow-up rate at 2 to 4 and 4 to 8 weeks? We would expect follow-up rate to be at least 80%, using various methods of contact.
 - IV. Proportion or women switching treatments: this will be the proportion of women randomised to a treatment that do not receive the assigned treatment.
- 2. To derive a realistic understanding of trial processes, in particular:
 - IV. Ascertain robustness of the data collection process during and after the surgical procedure. We would expect completeness of important miscarriage treatment technique and early complication data to be over 90%.
 - V. Determine the support required in units to ensure successful recruitment
 - VI. Why patients decline participation or withdraw after randomisation. The reasons why women declined should be captured on the screening log. This could allow changes to the protocol to make participation within the trial more acceptable.

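### Section 13.1 overstates the precision of the recruitment rate: 90 of 270 gives a 95% CI about 11.2 points wide, not about 10

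*Protocol*

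**What the plan says.** Section 13.1 (Sample Size) sets the target: "This study will aim to enroll 90 women". The numerical reason it gives is precision: "This number will allow us to measure the recruitment rate with 95% confidence interval (CI) width of approximately 10" per cent. The condition attached is "if we assume 270 will be eligible over six months recruitment and we recruit a third of these". Section 13.1 offers no other numerical basis for the target.

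Two other places bear on it:

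- Section 8.2 (Process outcomes) sets a criterion on the same proportion: "A conversion rate of less than 33% will be considered unrepresentative and not sufficient to sustain a large study".
- Section 6.1 (Recruitment) gives the only volume figure in the protocol: "320 surgical evacuations are performed on average per year (60 evacuations under local anaesthetic and 260 under general anaesthetic"). It does not say whether this is an average per hospital or a total over the participating sites. The same section aims for 90 participants in about six months.

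Section 3.2 sets a minimum of three hospitals.

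**The concern.** Section 13.1 fixes every input to the precision statement: numerator, denominator, proportion and confidence level. The width can be recomputed without any assumption, and it does not come out at 10 points. The difference is in the favourable direction, and this figure is the stated reason for choosing 90.

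The proportion also matters to the pilot. Section 8.2 judges feasibility against 33%, and the planning rate of one third sits on that threshold. Anyone weighing the result should have the correct width.

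A related gap is that 270 eligible women in six months is assumed and not derived. The reader cannot connect it to the 320 evacuations a year in Section 6.1, because that figure has no unit.

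**Working it through.** **Inputs.** From Section 13.1: 90 enrolled, 270 eligible, p = 90/270 = 1/3, 95% confidence. From Section 6.1: 320 evacuations a year and about six months of recruitment. From Section 3.2: at least three hospitals.

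**1. The plan's own figure.** The stated full width is about 10 points. The normal-approximation (Wald) interval gives:

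- standard error = √((1/3)(2/3)/270) = 0.0287
- half-width = 1.96 × 0.0287 = 0.0562
- full width = 2 × 0.0562 = 0.1125, that is 11.2 points

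The stated figure is not reproduced.

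**2. Other interval methods and readings, 90 of 270.**

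| Method or reading | Interval | Width (points) |
|---|---|---|
| Wald | 27.7% to 39.0% | 11.25 |
| Wilson | 28.0% to 39.2% | 11.18 |
| Agresti-Coull | 28.0% to 39.2% | 11.19 |
| Jeffreys | 27.9% to 39.1% | 11.20 |
| Clopper-Pearson | 27.7% to 39.3% | 11.57 |
| Wald with continuity correction | not listed | 11.62 |
| Width read as half-width (Wald) | | 5.6 |
| 90% interval instead of 95% (Wald) | | 9.4 |

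No 95% method gives 10, and neither alternative reading does. The nearest 95% results are about 11.2, so the interval is about 12% wider than stated (11.2/10 = 1.12).

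**3. What a width of 10 points would need.** n = (2/9) × (2 × 1.96/0.10)² = 341.5, so about 342 eligible women, or about 114 recruits at one third.

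**4. The link from 320 a year to 270 in six months.** 320/2 = 160 evacuations in six months for whatever unit the 320 describes.

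- *If 320 is per hospital:* three hospitals give 3 × 160 = 480 evacuations. 270 eligible is then 270/480 = 56% of them, and there is no contradiction. Three is a minimum, so 56% is the highest share needed on this reading; four hospitals would need 270/640 = 42%.
- *If 320 is the total for all sites:* at most 160 women could be eligible in six months, so 270 is impossible. One third of 160 is about 53 recruits, with a width of 2 × 1.96 × √((2/9)/160) = 14.6 points. Reaching 90 at that rate would take 90/(53.3/6) = about 10 months.

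The protocol does not say which reading applies.

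**The case against.** The strongest defence is that the text says approximately and the gap is small: 1.2 points in full width, or 5.6 against 5 in half-width. No decision turns on it. The 33% criterion in Section 8.2 is worded as a simple rate with no interval attached, and Section 13.2 makes the analyses mainly descriptive. At the planned result, 33% lies inside the interval whether its width is 10 points (28.3% to 38.3%) or 11.2. This defence stands as to consequence and keeps the severity low. It does not make the figure right, since 11.2 rounds to 11 and every input was available.

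Two stronger readings are tempting, and the documents support neither:

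- A reader might infer that 270 eligible women exceeds the available volume, so that 90 cannot be reached in six months. That requires the 320 to be the total for all sites. In a trial of at least three hospitals, an average per hospital fits the wording at least as well, and then nothing conflicts. Section 13.1 also presents 270 openly as an assumption. The 53 recruits, 14.6 points and 10 months all depend on the adverse reading.
- A reader might infer that variation in conversion between sites makes the interval wider still. The documents give no site-level conversion rates, and Section 13.1 claims only a simple interval for the recruitment rate. There is no basis here for an inflation factor.

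**Conclusion.** Wrong as written, at minor severity. On Section 13.1's own inputs the 95% CI width is about 11.2 percentage points (about 28% to 39%), so the stated precision is about 12% too favourable. This rests only on the protocol's figures and the usual binomial treatment of a single proportion, and it does not depend on the choice of interval method.

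That Section 6.1 gives no unit for the 320 and that 270 is not derived from it is a supporting point of clarity. It is not a demonstrated contradiction. It becomes an error in the recruitment plan only if 320 turns out to be the all-site total.

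**What to change.** In Section 13.1, replace the stated precision with *a 95% CI width of about 11 percentage points (about 28% to 39%)*. Leave enrolment at 90.

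In Section 6.1, state whether the 320 evacuations a year are per hospital or for all sites, and show the step from that figure to 270 eligible women in six months. If it is per hospital, give the number of hospitals and the share of evacuations expected to be eligible. If it is the total, restate the recruitment period and the width together: keeping six months gives about 14.6 points at best, while waiting for 270 eligible women takes about 10 months or longer and keeps about 11.2.

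The cost is wording only, with a slightly less favourable stated precision. No extra participants and no design change are needed unless 320 proves to be the total, in which case the timeline must be revisited.

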13.2. Statistical Analysis

The study size is too small to allow reliable analysis of the effect of the intraoperative ultrasound on outcomes. Analyses of feasibility and clinical outcomes will primarily take the form of simple descriptive statistics (e.g. proportions & interquartile ranges, means and standard deviations) and where appropriate, point estimates of effects sizes (e.g. mean differences and relative risks) and associated 95% confidence intervals. In the first instance, for clinical outcomes, participants will be kept in the groups they were allocated, regardless of compliance with treatment (intention-to-treat). A Statistical Analysis Plan will be generated for review by the Trial Oversight Committee before any analysis takes place.

13.3. Missing Data and Sensitivity Analyses

There is a potential for some missing data to occur at follow-up. However, in this context, this is part of the assessment of the success of the study and imputation of missing responses is not proposed.

13.4. Planned Interim Analysis

The Oversight Committee will meet prior to study commencement to agree the manner and timing of any analyses but this is likely to be limited due to the scope and timescales of the study recruitment period. If appropriate, criteria for stopping or modifying the study will be ratified by the Oversight Committee. Details of the agreed plan will be written into the Statistical Analysis Plan and the TOC charter. Further details of TOC arrangements are given in section 14.4.

13.5. Planned Final Analyses

The primary analysis for the study will occur once all participants have completed the hysteroscopy assessment (at 4-8 weeks post-procedure) and corresponding outcome data has been entered onto the study database and validated as being ready for analysis.

14. TRIAL ORGANISATIONAL STRUCTURE

14.1. **Sponsor**

The sponsor for this trial is the University of Birmingham.

14.2. Coordinating Centre

The trial coordinating centre is Birmingham Clinical Trials Unit, based at the University of Birmingham.

14.3. Trial Management Group

The Trial Management Group will take responsibility for the day-to-day management of the trial, and will include the CI, statistician and trial manager. The role of the group is to monitor all aspects of the conduct and progress of the trial, ensure that the protocol is adhered to and take appropriate action to safeguard participants and the quality of the trial itself.

